6.0 STATISTICAL CONSIDERATIONS

6.1 Study objectives and design

The primary objective is to compare the 1-year local control in patients with operable, recurrent previously-irradiated squamous cell head-and-neck cancers with or without adjuvant SBRT.

Secondary objectives include to determine the locoregional progression-free survival (PFS) distant PFS, overall PFS (local + regional + distant), and overall survival (OS); to evaluate the acute and late toxicities of adjuvant SBRT in the re-irradiation setting following salvage surgery; to determine prognostic factors that may predict the likelihood of local failure, regional failure, or OS in this cohort to guide future management; and to compare the impact of adjuvant SBRT versus a wait-and-see approach on patient reported quality of life (PR-QoL),

This clinical trial is planned as a prospective, randomized, two-arm Phase II study.

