SURGERY WITH OR WITHOUT STEROTACTIC BODY RADIOTHERAPY

A Prospective Randomized Phase II Study of Surgery with or without Adjuvant Stereotactic Body Radiotherapy (SBRT) in Patients with Previously-Irradiated Head and Neck Cancer

(Version Dated 2020-04-29)

Principal Investigator:

[name], PhD
UPMC Cancer Center
Mary Hillman Jennings Radiation Oncology Center
[name]
[name]
[name]
[contact]
Ph: [contact]
[contact]

Study Co-Investigators:

Radiation Oncology

[name] ([contact])
[name], PhD ([contact])
[name] ([contact])

Hematology Oncology

[name] [name] ([contact])

Otolaryngology

[name] [name] ([contact])
[name] ([contact])
[name] ([contact])
[name] ([contact])

Biostatistics

[name] ([contact])

TABLE OF CONTENTS

PROTOCOL SUMMARY	3
1.0 BACKGROUND	5
2.0 OBJECTIVES	7
3.0 INVESTIGATIONAL PLAN.....	8
4.0 SUBJECT SELECTION AND ELIGIBILITY.....	11
5.0 TREATMENT EVALUATION, ADMINISTRATION, AND MODIFICATION...	13
6.0 STATISTICAL CONSIDERATIONS.....	14
7.0 DATA SAFETY AND MONITORING.....	16
8.0 REFERENCES	17

PROTOCOL SUMMARY

Title

A Prospective Randomized Phase II Study of Surgery with or without Adjuvant Stereotactic Body Radiotherapy (SBRT) in Patients with Previously-Irradiated Head and Neck Cancer

Objectives

The *primary* objective of this study is to compare the 1-year local control in patients with operable, recurrent previously-irradiated squamous cell head-and-neck cancers with or without adjuvant SBRT.

The *secondary* objectives of this study are:

1. To determine the locoregional progression-free survival (PFS), distant PFS, overall PFS (local + regional + distant), and overall survival (OS).
2. To evaluate the acute and late toxicities of adjuvant SBRT in the re-irradiation setting following salvage surgery.
3. To determine prognostic factors that may predict the likelihood of local failure, regional failure, or OS in this cohort to guide future management.
4. To compare the impact of adjuvant SBRT versus a wait-and-see approach on patient reported quality of life (PR-QoL).
5. To compare surgical versus SBRT-induced immunological serum markers in relation to local control.

Patient population

In order to be eligible for this study, patients must have a pathologically proven recurrent or second-primary head-and-neck cancer with no evidence of distant metastases. Patients must be at least 18 years of age and able to give informed consent. They must have a Karnofsky Performance Status ≥ 60 .

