Number of patients

42

Study design and methodology

This is a prospective, double-arm phase II study. The treatment schema detail is in Section 6.3.

Treatment administered

Patients will or will not receive adjuvant Stereotactic Body Radiotherapy (SBRT) at various levels depending upon tumor volume. Subsequent evaluations will measure the efficacy of the adjuvant SBRT.

Efficacy data collected

The following evaluations will be performed to assess the efficacy of preoperative stereotactic radiation therapy:

- Objective local control rate measuring tumor volume
- Health Related Quality of Life assessment using the University of Washington Quality-of-Life-Revised (UW-Qol-R)

Safety data collected

The following evaluations will be conducted to assess the safety of radiosurgery:

- Recording of all toxicity data per NCI CTCAE version 4.0

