2.0 OBJECTIVES

Primary

- 2.1 To compare the 1-year local control in patients with operable, recurrent previously-irradiated squamous cell head-and-neck cancers with or without adjuvant SBRT.

Secondary

- 2.2 To determine the locoregional progression-free survival (PFS) distant PFS, overall PFS (local + regional + distant), and overall survival (OS).
- 2.3 To evaluate the acute and late toxicities of adjuvant SBRT in the re-irradiation setting following salvage surgery.
- 2.4 To determine prognostic factors that may predict the likelihood of local failure, regional failure, or OS in this cohort to guide future management.
- 2.5 To compare the impact of adjuvant SBRT versus a wait-and-see approach on patient reported quality of life (PR-QoL).

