4.3 Inclusion criteria

Each patient must meet all of the following inclusion criteria for study enrollment:

- Age ≥ 18 with ability to provide written informed consent
- Pathologically proven recurrent or second-primary head-and-neck cancer receiving prior radiotherapy with or without chemotherapy
- Prior radiotherapy to a dose of $\geq 50\text{Gy}$
- No evidence of distant metastases
- Macroscopic complete salvage surgery with curative intent (surgery was not performed only for biopsy or palliation). Final pathology and imaging must indicate a R0 or R1 resection (no gross disease remaining).
- High-risk pathologic features must be present: compromised/positive surgical margins ($\leq 2\text{mm}$) or extra-nodal extension (patient with other high-risk features gross perineural invasion, bone invasion, angiolytic invasion, or a constellation of these factors may be eligible based on case-by-case basis at discretion of principal investigator).
- Karnofsky Performance Status ≥ 60 (ECOG 0-2)

- Any number or type of prior chemotherapy is allowed (patient may receive concurrent or adjuvant systemic therapy such as cetuximab at the discretion of the treating oncologic team).

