5.0 TREATMENT EVALUATION, ADMINISTRATION, AND MODIFICATION

5.1 Primary outcome variables to be evaluated

- (1) Primary endpoint - local progression-free survival (LPFS), defined as the time from the date of randomization to the date of local progression or the date of death from any cause. Subjects who are alive and have not progressed will be censored at their last follow-up date.
- (2) Regional PFS, distant PFS, PFS (local + regional + distant): The definition of these endpoints is similar to LPFS.
- (3) Overall Survival: time from the date of randomization to the date of death due to any cause.
- (4) Acute and late toxicities of adjuvant SBRT. Acute toxicity is defined as toxicity occurring within 3 months of completion of SBRT. Late toxicity is defined as toxicity occurring later than 3 months after SBRT treatment.

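### The primary objective is 1-year local control, but the plan defines, sizes, tests and estimates LPFS, which counts every death

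*Combined protocol and SAP*

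**What the plan says.** **The objective.** Section 6.1 states: "The primary objective is to compare the 1-year local control in patients with operable". Section 2.1 reads: "To compare the 1-year local control in patients with operable, recurrent previously-irradiated squamous cell head-and-neck cancers with or without adjuvant SBRT". The Protocol Summary says the same.

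**The endpoint.** Section 5.1 names LPFS as primary and runs it from randomization "to the date of local progression or the date of death from any cause". Of the regional, distant and overall PFS endpoints it says "The definition of these endpoints is similar to LPFS", so on that wording these also count deaths.

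**Sizing and analysis.** Section 6.2 sizes the trial on one-year LPFS of 20% versus 52% with a one-sided log-rank test. Section 6.4 plans Kaplan-Meier estimates, one-year LPFS with a 95% confidence interval, a one-sided log-rank comparison of survival, and exploratory Cox models for survival.

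**Other text on local outcomes.** The Protocol Summary lists "Objective local control rate measuring tumor volume" among the efficacy data, and its secondary objective 5 is "To compare surgical versus SBRT-induced immunological serum markers in relation to local control". Objective 2.4 seeks prognostic factors for local failure, among other outcomes. Sections 3.6.4 to 3.6.6 give the imaging schedule, the measurement methods and a time origin for survival and time to progression.

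**The concern.** LPFS and local control are different quantities as soon as anyone dies without local failure. That patient is an LPFS event but has not failed locally. A trial run exactly to this plan would produce an LPFS result under an objective worded as local control, and its 90% power would be read as applying to local control.

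The rest of the plan does not close the gap. Local control has no event definition, time origin, censoring rule or handling of death. The tumor-volume line does not say what counts as loss of control in patients who enter after complete resection (4.3: "Final pathology and imaging must indicate a R0 or R1 resection (no gross disease remaining"). Section 6.4 does not say how death without local failure would be handled in any analysis of local failure.

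Two related gaps affect LPFS itself. Section 3.6.6 measures time to progression from salvage surgery, whereas 5.1 measures LPFS from randomization. Section 5.1 also gives no criterion for local progression, and in particular no boundary between local and regional recurrence.

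**Working it through.** **1. Objective against operative text**

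| Element | Where | Quantity |
|---|---|---|
| Primary objective | Summary, 2.1, 6.1 | 1-year local control |
| Primary endpoint | 5.1 | LPFS (deaths count) |
| Sample size and its test | 6.2 | LPFS |
| One-year estimate | 6.4 | LPFS |
| Between-arm test | 6.4 | survival endpoints |
| Analysis of local failure between arms | 6.4 | none specified |

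**2. The plan's own figure**

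Inputs from 6.2: one-year LPFS 20% and 52%, one-sided 0.10, power 90%, 1:1 allocation, 2-year accrual plus 1 year, 5% loss. Assumptions: exponential LPFS, uniform accrual, and loss read as 5% per year.

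- Hazards: −ln 0.20 = 1.609 and −ln 0.52 = 0.654 per year. HR = 0.654/1.609 = 0.406.
- Required events (Schoenfeld): 4(1.2816 + 1.2816)²/(ln 0.406)² = 32.4.
- Event probability: (λ/h)[1 − (e^−h − e^−3h)/(2h)], where h = λ − ln 0.95. This gives 0.916 (control) and 0.682 (SBRT), mean 0.799.
- N = 32.4/0.799 = 40.6, so 21 per arm. **The plan's figure reproduces.**
- With 42 patients: 21 × (0.916 + 0.682), about 33.5 events. Schoenfeld power is 0.908; a log-rank simulation (20,000 trials) gave 0.897.

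**3. What that implies for local failure**

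Let s be the share of control-arm LPFS events that are deaths without local failure. The documents give no value, so every row below is an assumption. LPFS is held at 20% versus 52% throughout. One-year cumulative incidence of local failure = (local hazard/total hazard) × (1 − one-year LPFS).

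- (a) SBRT does not affect those deaths. The death hazard is 1.609s in both arms, and the SBRT local hazard is 0.654 − 1.609s. This is possible only for s below 0.654/1.609 = 0.406.
- (b) SBRT reduces those deaths as much as local failure, so both hazards have HR 0.406.

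Example, (a) with s = 0.2: the control local hazard is 0.8 × 1.609 = 1.288, and the SBRT local hazard is 0.654 − 0.322 = 0.332, so the local HR is 0.258. Local failure at one year is 0.8 × 0.80 = 64% versus (0.332/0.654) × 0.48 = 24%.

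| Scenario, s | Local failure at 1 year | Difference (points) | Local events | Power: Schoenfeld / simulated |
|---|---|---|---|---|
| (a) 10% | 72% v 36% | 36 | 28.1 | 0.942 / 0.936 |
| (a) 20% | 64% v 24% | 40 | 22.7 | 0.974 / 0.967 |
| (a) 30% | 56% v 13% | 43 | 17.2 | 0.996 / 0.991 |
| (b) 10% | 72% v 43% | 29 | 30.2 | 0.884 / 0.876 |
| (b) 20% | 64% v 38% | 26 | 26.8 | 0.853 / 0.844 |
| (b) 30% | 56% v 34% | 22 | 23.5 | 0.816 / 0.801 |
| (b) 50% | 40% v 24% | 16 | 16.8 | 0.713 / 0.696 |

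Power is for the cause-specific log-rank test at one-sided 0.10. The same LPFS result is compatible with one-year local-failure differences from 16 to 43 points in these examples. They are not bounds.

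**4. Precision of a local-failure estimate**

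The 95% half-width of the one-year difference is about 1.96 × √{[p₀(1−p₀) + p₁(1−p₁)]/21}. Across the rows this is 0.255 to 0.293; simulation of the cumulative-incidence estimator gave 0.255 to 0.302. For one-year LPFS itself the formula gives 0.274.

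**The case against.** **LPFS is simply how the protocol operationalises local control.** Section 6.2 follows 6.1 directly, and 5.1 gives the event and the censoring rule. This is the natural reading of what the authors meant to do, and it makes the fault one of wording rather than of design. It does not remove the fault: no passage makes the link, and the label hides the deaths.

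**The plan is not silent on local outcomes.** This stands. A reader might infer that nothing in the documents bears on measuring or analysing local failure. Sections 3.6.4 to 3.6.6 cover imaging, measurability and objective progression, the Summary lists a local control rate among the data collected, and objective 2.4 names local failure as an outcome. None of these defines local control. The Cox sentence in 6.4 includes treatment, but it is exploratory and about survival. Even read broadly, it gives no rule for death without local failure.

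**No harm is demonstrated.** This stands too. A reader might infer that the trial is underpowered for local control, or that LPFS distorts the local effect in a known direction. The documents support neither: the scenarios fall on both sides of 90%, and the share of deaths without local failure is unknown.

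**A competing-risk analysis is optional in a 42-patient phase II trial.** Fair. It is good practice and inexpensive, but the wording correction is the necessary part.

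**Conclusion.** The inconsistency is in the text and should be corrected. The stated primary question is 1-year local control, and the specified primary analysis answers an LPFS question. The sample size is right for LPFS (about 33.5 events and about 90% power, assuming exponential times and 5% loss per year). For local control the power is not established and could be higher or lower.

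A reader might also infer from the correct sizing that the primary LPFS analysis is free of ambiguity. It is not, because the two time origins conflict and local progression has no criterion.

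The mismatch does not depend on any assumed death rate; only the illustrative figures do.

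**What to change.** **Necessary**

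- In the Summary, 2.1 and 6.1, restate the primary objective as comparing LPFS between arms by one-sided log-rank test, with one-year LPFS by arm and 95% confidence intervals. Do not describe the LPFS result as local control. Saying only that LPFS assesses local control would leave that label on an endpoint that counts deaths.
- Reconcile the time origin in 3.6.6 (salvage surgery) with 5.1 (randomization).
- In 5.1, state a criterion for local progression, including how local and regional recurrence are separated after complete resection, and use the same event for local failure.
- Align Summary secondary objective 5 and the tumor-volume line with that definition.
- Keep N = 42, the endpoint and the primary test.

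**Recommended**

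In 6.4, add a descriptive analysis, stated as not separately powered: cumulative incidence of local failure by arm with death without local failure as a competing event, the one-year difference, and the cause-specific hazard ratio, each with a 95% confidence interval. Base any statement about local control on it.

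**Cost**

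The changes are wording in the places named, one definition, and one analysis of dates already needed for LPFS, with no added visits. The price is a narrower primary claim. The local-failure estimate would rest on about 17 to 30 events with an interval of roughly ±26 to 30 points (illustrative). It can describe the local component but cannot show how far deaths drive the LPFS effect.

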6.2 Sample size and accrual rate

Forty (40) patients will be screened for each arm of the trial so that 21 subjects will be cleared to participate in research procedures in each arm of the trial.

The following assumptions are used in determining the sample size for this study:

Primary endpoint: local progression-free survival (LPFS)

One-sided type I error rate: 0.10

Statistical power: 90%

One-year LPFS for surgery alone: 20%

One-year LPFS for surgery + SBRT: 52%

Randomization: 1:1

2-year accrual period and one year follow-up following closure of accrual

5% lost to follow-up in each arm

To have 90% power to detect the above 32% difference in one-year LPFS, using a onesided log-rank test with a 0.1 level of significance, 21 patients are required in each arm.

The randomization of subjects to one of the two treatment arms will be in a 1:1 ratio. The UPCI Biostatistics Facility has a randomizer, an intranet application for randomly assigning patients to different treatments, which will be used for the randomization in this trial.

6.3 Statistical approach and analysis

(1) Efficacy Analysis Set: includes all enrolled and randomized patients. Subjects will be analyzed according to their randomized treatment group assignment.

(2) Safety Analysis Set: The safety analysis will be performed according to the actual treatment received.

6.4 Analysis of primary and secondary endpoints

Survival endpoints will be estimated by the Kaplan-Meier method and the corresponding median survival times (with 95% confidence interval) reported. The one-year LPFS will also be estimated along with its 95% confidence interval. Survival will be compared between the two arms with the one-sided log-rank test. Effect of treatment and other variables (e.g., baseline characteristics, biomarkers etc) on survival will be explored with Cox regression models.

For the quality of life (QoL) data analysis, each item of the UW-QoL-R will be individually assessed. The mean and standard deviation of the observed data will be summarized at each collection time and plotted against time, from baseline through the end of patient follow-up. Generalized linear models (such as cumulative logit models) for repeated measures will be used to explore if there are significant changes in PR-QOL over time.

Using NCI Common Terminology Criteria for Adverse Events (CTCAE v4.0), the number of patients experiencing adverse events over their course of treatment will be characterized by type of adverse event and grade, by the time of onset in relation to the first day of therapy, and whether the event is clinically significant. Attribution of adverse events to treatment (unrelated, unlikely, possibly, probably, or definitely) will also be summarized for any serious adverse events (SAEs), CTCAE grade 3 or higher. The percentage of patients experiencing SAEs that are considered to be treatment-related (probable or definite) will be determined. The percentages of patients experiencing the acute/late toxicities associated with SBRT will also be estimated along with their exact 95% confidence intervals.

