1.2 Adjuvant Re-Irradiation

The only phase III experience evaluating adjuvant therapy after surgical salvage is from the Institute Gustave-Roussy (7). In this phase III study, 130 previously-irradiated rHNC patients were randomized following salvage surgery to chemotherapy + re-irradiation (CT/Re-RT) versus observation. Chemotherapy consisted of six cycles of hydroxyurea and continuous infusion 5-FU, while adjuvant re-irradiation was delivered to a total dose of 60 Gy in a split-course fashion (the contemporaneous RTOG standard). Disease-free survival (DFS), but not overall survival (OS), was improved with the addition of adjuvant CT/Re-RT (the study was not powered for OS). However, this treatment was not without toxicity. Grade 3 or 4 mucositis was seen in 28% of patients and 39% of patients had grade 3 or 4 late toxicity versus only 10% of patients in the observation arm. This is the only level I evidence for adjuvant therapy in re-irradiation setting. Thus the data supports the role of re-irradiation in improving local control albeit with the expense of significant toxicity.

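### The one-sided log-rank test in section 6.4 is not limited to LPFS, so the planned between-arm test of overall survival cannot separate no effect from harm

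*Combined protocol and SAP*

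**What the plan says.** Section 5.1 lists five time-to-event endpoints: LPFS (named as primary), regional PFS, distant PFS, PFS over all sites, and OS. OS is defined as "Overall Survival: time from the date of randomization to the date of death due to any cause".

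Section 6.2 sizes the trial on LPFS alone and lists "One-sided type I error rate: 0.10" among the assumptions for that calculation. No significance level is given for any other endpoint, and there is no multiplicity rule.

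Section 6.4 begins with Kaplan-Meier estimation of the survival endpoints as a group, with medians and 95% confidence intervals, and adds an interval for one-year LPFS. It then says "Survival will be compared between the two arms with the one-sided log-rank test". Cox models for treatment and other variables are to be explored, with no sidedness and no hazard-ratio interval stated. No other between-arm test of survival is planned.

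**The concern.** The word survival in section 6.4 can be read broadly, as all five endpoints, or narrowly, as OS alone. OS falls under the one-sided test either way. A one-sided 0.10 test is a reasonable screening choice for the endpoint that was sized. It is less suitable for OS, where the direction of harm matters to anyone deciding whether to take re-irradiation further.

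The protocol's background makes harm worth checking. In the randomized trial of post-salvage re-irradiation with chemotherapy described in section 1.2, "39% of patients had grade 3 or 4 late toxicity versus only 10% of patients in the observation arm", and OS was not improved. If SBRT shortened survival here, the planned test would report no significant difference, the same result as for no effect.

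A second, smaller issue follows. If the 0.10 level is carried over to the four unsized endpoints and each is read as a test, the chance of at least one false positive rises above 10%.

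**Working it through.** **Step 1: reproduce the stated sample size.** Inputs from section 6.2: one-year LPFS 20% versus 52%, one-sided 0.10, power 90%, 1:1 allocation, 2 years of accrual plus 1 year of follow-up, 5% loss, 21 per arm.

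- Exponential hazard ratio: ln 0.52 / ln 0.20 = 0.406.
- Events (Schoenfeld): 4 × (1.2816 + 1.2816)² / (ln 0.406)² = 32.4, rounded up to 33.
- Probability of an event at hazard λ, with uniform accrual: 1 − (e^(−λ) − e^(−3λ)) / (2λ). This gives 0.940 for control and 0.710 for SBRT, mean 0.825.
- Patients: 33 / 0.825 = 40.0, and 40.0 / 0.95 = 42.1.

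The planned 42 reproduces, with power of 90.4%. The one-sided 0.10 level therefore belongs to the LPFS calculation.

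**Step 2: what an OS comparison could show if SBRT were harmful.** The documents give no OS rate. I assume exponential survival with a control death hazard of 0.7 per year, and use the plan's 21 per arm and its accrual and follow-up, with no loss. I also assume that the one-sided alternative favours SBRT, as the sample-size section implies.

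Expected deaths D are 42 times the mean event probability. The expected standardized log-rank statistic in the direction of harm is d = ln(HR) × √D / 2. A two-sided 5% test shows harm with probability Φ(d − 1.96).

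| True OS HR | Mean event probability | D | d | Φ(d − 1.96) | Simulated |
|---|---|---|---|---|---|
| 1.5 | 0.793 | 33.3 | 1.17 | 21.5% | about 21% |
| 2.0 | 0.825 | 34.7 | 2.04 | 53.2% | about 51% |
| 2.5 | 0.842 | 35.4 | 2.73 | 77.8% | about 77% |

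The formula and the simulated trials agree closely. At HR 2.0, simulated control hazards from 0.4 to 1.0 per year give 43% to 57%.

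The one-sided test rejects only for benefit, so it shows harm in 0% of trials at every hazard ratio. At HR 2.0 it falsely rejects for benefit with probability Φ(−1.2816 − 2.04), below 0.1%. It therefore gives p > 0.10 in more than 99.9% of trials.

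**Step 3: false positives if all five endpoints were tested at one-sided 0.10.** The plan gives neither the level for the secondary tests nor the correlation between them, so both are assumptions.

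- Independent tests: 1 − 0.9⁵ = 41.0%.
- Common correlation 0.3, 0.5, 0.7, 0.9: 34.0%, 29.2%, 24.0%, 17.4%.
- Simulated null trials, 21 per arm, death counted in every endpoint: 21% to 33%, depending on the hazards assumed for progression and death.
- At 0.05 for every test instead: 1 − 0.95⁵ = 22.6% if independent, and about 12% to 15% in simulation.
- If only LPFS is confirmatory: 10%.

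The tests are clearly correlated, because death is an event in all five endpoints and overall PFS contains the others. Independence is therefore an upper reference, not a likely value.

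**The case against.** The strongest objection is that harm would not be hidden. Section 6.4 plans Kaplan-Meier estimates with 95% intervals for the medians and an exploratory Cox model that includes treatment. Serious adverse events are to be summarized with attribution, acute and late toxicity rates carry exact intervals, and section 7.1 provides for monthly toxicity review. A doubled death hazard would probably be visible in the curves. A reader might infer from the one-sided test that a survival detriment could never be recognized or reported, and the documents do not support that. The limitation applies to the log-rank test. What remains is that no interval for the between-arm OS effect is specified, and the Cox model has no stated form of reporting.

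The background evidence is also indirect. The trial in section 1.2 gave split-course re-irradiation with chemotherapy, improved disease-free survival, was not powered for OS, and is not reported to have shown an OS detriment. Section 1.4 argues that SBRT is less toxic than conventional re-irradiation. This makes harm a possibility to allow for, not an expectation. The gain from a two-sided comparison is also modest at HR 1.5, where it shows harm in only about one trial in five.

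On multiplicity, a reader might infer a definite false-positive rate of about 30%. That figure needs 0.10 on every secondary test and a correlation near 0.5, and the documents state neither. One primary endpoint is named, the secondary survival objective is worded as estimation, and no claim is tied to it. Unadjusted secondary analyses are ordinary in a 42-patient phase II trial. This part of the objection largely stands. However, nothing in the plan labels the secondary endpoints descriptive, and section 5.1 lists them under a heading about primary outcome variables.

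**Conclusion.** The point holds in a limited form. The one-sided log-rank test extends to OS without justification. As the only planned between-arm test of OS, it gives the same answer for no effect and for harm. A two-sided 5% comparison would show harm in about 21%, 51% and 77% of trials at OS hazard ratios of 1.5, 2.0 and 2.5. Those figures assume exponential survival, a control death hazard of 0.7 per year and a one-sided alternative that favours SBRT.

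The chance of at least one false positive across five one-sided 0.10 tests is roughly 17% to 41%, depending on the assumed correlation, and lower at a stricter level. It matters only if secondary results are read as claims.

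The LPFS test and the sample size are not affected. This is a cheap improvement to the analysis text, not a flaw in the primary analysis.

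**What to change.** In section 6.4, state that the one-sided 0.10 log-rank test applies to LPFS only. For OS, regional PFS, distant PFS and overall PFS, report the hazard ratio with a two-sided 95% confidence interval, and make any p-value two-sided and nominal. Label these results descriptive and say that no efficacy claim rests on them.

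The cost is about two sentences of text and less favourable secondary p-values. The 42 patients and the LPFS power stay as they are. Making the LPFS test two-sided is not proposed: at 42 patients its power would fall from 90.4% to 82.6% at two-sided 0.10, or 73.4% at two-sided 0.05.

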3.6.6 Evaluation of Disease Status and Survival

Survival and time to progression will be measured from the date of salvage surgery to date of death, appearance of new metastatic lesion, or objective tumor progression.

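### Objective 2.4 asks what predicts local failure and regional failure, but the Cox models in 6.4 do not model either one separately from death

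*Combined protocol and SAP*

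**What the plan says.** Section 2.0, item 2.4, states the objective: "To determine prognostic factors that may predict the likelihood of local failure, regional failure, or OS in this cohort to guide future management". The protocol summary and section 6.1 repeat it. Because OS is listed separately, failure and death are treated as different outcomes.

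Section 5.1 defines the endpoints:

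- LPFS runs from randomization to "the date of local progression or the date of death from any cause".
- For regional PFS, distant PFS and overall PFS, "The definition of these endpoints is similar to LPFS".
- OS is the "time from the date of randomization to the date of death due to any cause".

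Section 3.6.6 offers no alternative: "Survival and time to progression will be measured from the date of salvage surgery to date of death", new metastasis or progression.

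On analysis, section 6.4 says "Survival endpoints will be estimated by the Kaplan-Meier method", compares the arms with the log-rank test, and adds for prognostic factors: "Effect of treatment and other variables (e.g., baseline characteristics, biomarkers etc) on survival will be explored with Cox regression models". Neither 6.4 nor any other section mentions a cause-specific, cumulative-incidence or other competing-risk method.

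**The concern.** The word survival in the Cox sentence can be read in two ways, and neither delivers objective 2.4. If it means OS, local and regional failure have no model. If it means the time-to-event endpoints of 5.1, the local and regional models are fitted to composites in which every death is an event. The coefficient then describes failure and death together.

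Two errors follow if such a coefficient is read as an answer to 2.4. A factor related only to death, perhaps performance status, can appear to predict local failure. A factor that truly predicts local failure has its effect pulled towards 1 by deaths it does not influence. Regional PFS is more exposed still: a patient who fails locally, never fails regionally and then dies is a regional PFS event.

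The objective gives guidance of future management as its purpose. Predictors of local failure and predictors of death have different uses, and the plan as written cannot tell them apart.

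**Working it through.** **1. The plan's own figure.** Inputs from section 6.2: one-year LPFS 20% and 52%, one-sided 0.10, power 90%, two years' accrual plus one year of follow-up, 5% loss per arm.

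- With exponential hazards, HR = ln(0.52)/ln(0.20) = 0.654/1.609 = 0.406.
- Schoenfeld events = 4 × (1.2816 + 1.2816)² / (ln 0.406)² = 26.28/0.811 = 32.4, so 33.
- With uniform accrual, and the loss taken as 5% per year (an assumption), the average event probability is 0.799. Then 33/0.799/2 = 20.7, so 21 per arm, as stated.
- Expected LPFS events from 42 patients: 42 × 0.799 = 33.5.

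The sample size is reproduced, and nothing below changes it.

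**2. A factor that acts only on death.** Let s be the share of the LPFS hazard due to death without local failure. The documents do not give s, so 10%, 30% and 50% are assumed. Let a factor with 50% prevalence multiply that death hazard by h = 2 or 3 and leave local failure unchanged. The LPFS hazard ratio depends on where s is anchored:

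- Set-up A (s midway between the two factor groups): HR = [(1−s) + s√h] / [(1−s) + s/√h].
- Set-up B (s in the group without the factor): HR = 1 + s(h−1).

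| s | A: h = 2, h = 3 | B: h = 2, h = 3 |
|---|---|---|
| 10% | 1.07, 1.12 | 1.10, 1.20 |
| 30% | 1.23, 1.40 | 1.30, 1.60 |
| 50% | 1.41, 1.73 | 1.50, 2.00 |

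Simulated medians across set-ups are about 1.1-1.2, 1.2-1.7 and 1.4-2.1. The true hazard ratio for local failure is 1.0 by construction.

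**3. How often the factor is flagged.** Section 6.4 gives no significance level for the Cox models, so two-sided 5% is assumed. Trials of 42 patients were simulated (1,000 per setting for set-up A), with arm-adjusted Cox models. With set-up A, the LPFS model flags the factor in 5%, 11% and 16% of trials (h = 2; s = 10%, 30%, 50%) and in 7%, 15% and 36% (h = 3). A further simulation with about 36 LPFS events gives 7-8%, 14-28% and 24-55%. The cause-specific local-failure model flags it in about 4-6%.

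A hand check agrees. For HR 1.73 and 33.5 events, z = ln(1.73) × √(33.5/4) = 0.549 × 2.894 = 1.59, and Φ(1.59 − 1.96) = 0.36.

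**4. A true local-failure predictor.** If a factor doubles local failure and has no effect on death, the LPFS hazard ratio with s in the reference group is s + 2(1−s): 1.7 at 30% and 1.5 at 50%. Simulation gave 1.69 and 1.53, against about 2.0 from the cause-specific model. Detection was 33% against 40% at the 30% share, and 22% against 30% at the 50% share (LPFS first).

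**5. The cost in events.** With set-up A and about 33.5 LPFS events, local failures number about 30, 23 and 17 at death shares of 10%, 30% and 50%. Across all simulated settings the contrast is about 14-34 local failures against about 36 LPFS events. For a factor that doubles both hazards, power was 0.51, 0.48 and 0.47 with LPFS and 0.45, 0.34 and 0.24 with the cause-specific model.

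**The case against.** The strongest reply is that little rests on this analysis. It is described as exploratory, serves an unpowered secondary objective in 42 patients, carries no stated significance level and feeds no decision rule. An LPFS model reported as LPFS is a valid composite analysis, and the error arises only if its result is labelled local failure. All of this stands, and it limits the weight of the point.

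The distortion also depends on an unknown share. At 10% it is close to nothing. Section 1.1 reports recurrence approaching 100% after close or positive margins, a main eligibility feature, which suggests few deaths without any recurrence. But that figure does not separate local from regional or distant recurrence. A patient who dies of distant disease with local control is still an LPFS event, so the share remains open.

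The cause-specific model has its own price: it loses power for factors that raise both failure and death. Nor does a cause-specific hazard ratio alone describe the likelihood named in 2.4. A factor that only raises deaths has a cause-specific ratio near 1 but lowers the cumulative incidence of local failure. Both points stand, and the second is why cumulative incidence belongs in the fix.

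A reader might infer that local and regional failure are never modelled at all. The documents do not support that as a general statement: if the Cox sentence covers the 5.1 endpoints, failures enter as components of LPFS and regional PFS. A reader might also infer that the trial will report predictors of death as predictors of local failure. The plan does not say so; it only provides no means of telling them apart.

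**Conclusion.** The gap is real. Objective 2.4 names three outcomes, every candidate endpoint in 5.1 counts death, and 6.4 specifies no method that separates failure from death. The effect ranges from negligible at a 10% share of deaths without local failure to substantial at 50%. At the upper end, a factor unrelated to local failure could show an LPFS hazard ratio of about 2 and be flagged in up to about half of trials.

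These sizes rest on assumptions that the documents do not supply: the death share, a 50% prevalence, a factor that doubles or triples death alone, exponential hazards and a two-sided 5% level. The mismatch between objective and model does not depend on them. It is a low-cost improvement to consider, not a flaw in the trial's main comparison.

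**What to change.** Add to section 6.4 wording such as:

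*For objective 2.4, prognostic factors for local failure and for regional failure will be explored with cause-specific Cox models adjusted for randomized arm. The event is the first local, or the first regional, failure. Patients who die without that failure are censored at death. An earlier failure at the other site does not end follow-up for the site being modelled. The cumulative incidence of each failure type, with death as a competing event, will be reported alongside. Models for OS and for the composite PFS endpoints will be reported under those names.*

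This takes a few sentences and two extra models, and no more patients. Progression and death dates are already needed for 5.1. The regional model also needs regional failures recorded after a local one; section 3.6.4 follows patients for 24 months or until death and does not stop at progression. The statistical cost is wider intervals, and lower power for factors that raise both failure and death. Keeping the composite and OS models alongside limits that loss.
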